15.1.2 Adverse Events Leading to Discontinuation of Study Intervention

The overall summary of AEs leading to discontinuation of study intervention will include the frequency (number and percentage) of participants with each of the following, split by cohort and study intervention group:

CONFIDENTIAL

- TEAEs leading to permanent discontinuation (drug withdrawn)
- Related TEAEs leading to permanent discontinuation (drug withdrawn)
- TEAEs leading to temporary discontinuation (drug interrupted)
- Related TEAEs leading to temporary discontinuation (drug interrupted)

INFORMATION

A frequency table of TEAE leading to permanent discontinuation of study intervention will also be provided by primary SOC in alphabetical order and, within SOC, sorted by PT in decreasing incidence overall.

15.2 Deaths, Other Serious Adverse Events, and Other Significant Adverse Events

15.2.1 Deaths

Death date and reason for death are collected on the "DEATH" CRF form.

A participant data listing including date and reason of death, PT of AEs with fatal outcome together with selected dosing information (date of first/last administration) will be provided.

15.2.2 Serious Adverse Events

The following frequency tables will be prepared for serious TEAEs:

- Incidence of serious TEAEs by SOC and PT (*)
- Incidence of related serious TEAEs by SOC and PT (*)

A listing of SAEs will also be provided with the relevant information with a flag for SAEs with onset outside the on-treatment period.

15.2.3 Other Significant Adverse Events

The following events are defined as AE of Special Interest (AESI) as per protocol and will be included in Tier 1:

• Severe infections NCI-CTCAE grade ≥ 3

AESI will be identified using the corresponding flag entered in the "Adverse Event" eCRF page. In order to define the category to which they belong, SMQs or primary SOC will be used depending on the AESI (see table below).

Details of derivation for AESI categories are explained below:

AESI categories	Derivation
Severe infections	Primary SOC = 'Infections and Infestations' - Severe events only (i.e., ≥ Grade 3)
CCI	

AESI will be summarized as part of the 3-tier approach described in section 15.1.1 at primary analysis of Cohort A and final analyses of Cohort B.

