2.3.1 Risk Assessment

The clinical experience with enpatoran is limited to 3 completed studies in healthy participants (MS200569_0001, MS200569_0005, MS200569_0040), 1 completed Phase 2 study in participants with COVID-19 pneumonia (MS200569_0026), 3 ongoing studies in SLE or CLE (MS200569_0004, MS200569_0003 and the LTE study MS200569_0048, which will enroll participants completing 24 weeks treatment in MS200569_0003). There is no similar class product available on the market.

he AEs consistent with conditions ascribed as potential risks will be closely monitored and reported as AESIs during the clinical development, e.g., severe infection, CCI All study

participants will be made aware of signs and symptoms pertaining to contemplated potential risks and advised to report any adverse experiences throughout the study.

Table 2 Potential Risks of Clinical Significance^a

Identified and Potential Risks of Clinical Significance	Summary of Data/Rationale for Risk	Mitigation Strategy
	Study Intervention	
Severe Infections (≥ Grade 3)	Based on MOA, the TLR 7/8 inhibition increases the susceptibility to infection with ssRNA virus. No clinical experience of severe infection or other enpatoran exposure-dependent AE occurrence was reported across clinical studies.	 Exclude participants with ongoing or active clinically significant viral, bacterial or fungal infection (see exclusion criteria). Clinical evaluation for infection including SARS-CoV-2 (per local guidelines) before Day 1 of the dosing. SoC vaccinations should be up to date as per local guidance. Participant education to identify signs and symptoms of infection and seek appropriate medical attention (management and treatment) per institutional guidelines.

Enpatoran (M5049) The WILLOW study with enpatoran in SLE and CLE (SCLE and/or DLE) MS200569_0003

	T	
Identified and Potential Risks of Clinical Significance	Summary of Data/Rationale for Risk	Mitigation Strategy
CCI		
CCI		
		' = = = =

Identified and Potential Risks of Clinical Significance	Summary of Data/Rationale for Risk	Mitigation Strategy
CCI		

Identified and Potential Risks of Clinical Significance	Summary of Data/Rationale for Risk	Mitigation Strategy
CCI		

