8.3.7 Adverse Events of Special Interest (AESI)

An AESI (a serious or non-serious AEs deemed related to the study intervention) is one of the scientific and medical concern specific to the study intervention i.e., enpatoran, for which ongoing monitoring, and prompt communication by the study Investigator to the Sponsor is required. Such AEs of interest may warrant further investigations and in-depth evaluation to better characterize and understand the association between the AE and study intervention. Based on the enpatoran mode of action and findings of nonclinical toxicology studies, the following clinical experiences are considered as AESIs:

Upon observation of AE that qualifies to be an AESI, the Investigator must complete an AESI report Form and communicate the event/s with the Sponsor within 24 hours of occurrence of any AESI. AESI classified as serious based on SAE reporting criteria should always be reported as SAE as outlined in Section 8.3.3.

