15.1.1 All Adverse Events

Description of the Three-tier Analysis Approach

The 3-tier approach for summarizing and analyzing AEs in clinical studies will be followed. AEs in different tiers are analyzed using different types of statistical analysis.

Pre-specified AESI will be analyzed as part of Tier 1 if they fulfill the rule-of-4 (at least 4 participants in any of the study intervention groups). Otherwise, such AEs will be included in Tier 3. The pre-specified terms considered for Tier 1 are (see section 15.2.3 for further details):

•	Severe infections NCI-CTCAE grade ≥ 3 and all-related F	PTs

All of these prespecified events will be summarized in a table. Incidence rate and difference in incidence rate between each active group and placebo will be provided. A 95% CI for the difference in incidence rate will be provided for prespecified events fulfilling the rule-of-4 only. CI will be estimated using Miettinen & Nurminen method.

All TEAEs (unique preferred terms) will be classified as belonging to Tier 2 or Tier 3 and summarized in a table. Incidence rate and difference in incidence rate between each active group and placebo will be provided. A 95% CI for the difference in incidence rate will be provided for adverse events fulfilling the rule-of-4 only. CI will be estimated using Miettinen & Nurminen method.

Only TEAEs with at least one study intervention group with incidence proportion \geq 5% will be presented in the body of the CSR.

Statistical Outputs

The following tables will be provided:

- Overview of TEAEs including (*):
 - o TEAEs
 - o TEAEs, Grade ≥ 2 , Grade ≥ 3 , Grade ≥ 4
 - o Related TEAEs

- o Related TEAEs, Grade ≥ 2 , Grade ≥ 3 , Grade ≥ 4
- Serious TEAEs
- Non-serious TEAEs
- Related Serious TEAEs
- o TEAEs leading to death
- o Related TEAEs leading to death
- Prespecified Tier 1/3 TEAEs (displayed by term including incidences, risk differences and respective confidence limits for the difference in group incidence proportions, as applicable according to rule-of-4) as described above per the 3-tier analysis approach (see description of the 3-tier approach above)
- Tier 2 and Tier 3 TEAEs (displayed by PT including incidences, risk differences and respective confidence limits for the difference in group incidence proportions, as applicable according to Rule-of-4) as described above in the 3-tier analysis approach (see description of the 3-tier approach above)
- TEAEs by SOC and PT (*)

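### Severe-infection AESIs are selected by an investigator-entered flag whose protocol meaning is inconsistent on causality, so Grade ≥ 3 infections judged unrelated may be left out of the Tier 1 comparison

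*SAP*

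**What the plan says.** **Selection.** SAP 15.2.3 names severe infections of CTCAE Grade ≥ 3 as an AESI that goes into Tier 1. Events are picked by the flag: "AESI will be identified using the corresponding flag entered in the" adverse event eCRF page. Classification comes second: "In order to define the category to which they belong, SMQs or primary SOC will be used depending on the AESI". The rule for the infections category is "Primary SOC = 'Infections and Infestations' - Severe events only (i.e., ≥ Grade 3"), with no causality term.

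**What the flag means.** Protocol 8.3.7: "An AESI (a serious or non-serious AEs deemed related to the study intervention) is one of the scientific and medical concern". The investigator decides whether an event counts: "Upon observation of AE that qualifies to be an AESI, the Investigator must complete an AESI report Form". Protocol 2.3.1 is worded differently: "AEs consistent with conditions ascribed as potential risks will be closely monitored and reported as AESIs during the clinical development, e.g., severe infection". That sentence sets no causality condition.

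**What is then analysed.** SAP 15.1.1: "Pre-specified AESI will be analyzed as part of Tier 1 if they fulfill the rule-of-4", meaning at least 4 participants in any study intervention group; otherwise the event moves to Tier 3. The planned output is the incidence in each group and the difference from placebo for each active group. A 95% Miettinen-Nurminen interval is added only when the threshold is met. For details of the Tier 1 terms, 15.1.1 refers back to 15.2.3. Occurrence of AESIs is a secondary safety endpoint in protocol section 3 and SAP section 5.

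**The concern.** The flag is the entry gate and the class-and-grade rule works only behind it, so that rule cannot bring in an infection that was never flagged. If the flag is set according to protocol 8.3.7, a blinded causality judgement decides which severe infections enter a randomised comparison. Participants take background lupus therapy, which includes immunosuppressants and corticosteroids, and protocol Appendix 4 tells investigators to weigh concomitant therapy as an alternative cause. A reason to call an infection unrelated will often be at hand.

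Three things are at stake. A placebo-controlled comparison needs no individual causality judgement, and filtering on one throws away information. If the same share of events is lost in every arm, the rates and the risk difference shrink together. And if enough events are lost, the threshold of four is missed and no interval is produced. Because the protocol gives two descriptions of an AESI, the flag may also mean different things at different sites, among roughly 170 planned.

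**Working it through.** **1. The texts side by side**

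| Question | Protocol 8.3.7 | Protocol 2.3.1 | SAP 15.2.3 |
|---|---|---|---|
| Must the event be judged related? | Yes, in the definition | No condition stated | Not stated; inherits whatever the flag means |
| Who decides? | Investigator | Not stated | Investigator, through the flag |
| Role of class and grade | None visible | None | Sorts flagged events |

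For a Grade ≥ 3 infection judged unrelated, a site working from 8.3.7 does not flag it and it is absent from Tier 1. A site working from 2.3.1 flags it and it is counted. Neither document gives a second, data-driven route into the Tier 1 table.

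**2. Where such an event still appears**

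It is in the table of treatment-emergent events by SOC, preferred term and worst grade (SAP 15.1.1, also planned for the Cohort A primary analysis), in the Tier 2/3 tables by single preferred term and, if serious, in the SAE tables (SAP 15.2.2). The SOC-by-grade and SAE tables specify no risk difference or interval, and the Tier 2/3 differences are for one preferred term at a time. No other planned table gives a pooled Grade ≥ 3 infection risk difference with an interval.

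**3. Size, as an illustration only**

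The documents give no expected severe-infection rate and no share judged related, so there is no plan figure to reproduce. Let p be the true Grade ≥ 3 infection rate, taken as equal in all arms, and f the share of affected participants who are flagged. Both are assumptions.

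*Dilution.* With the same f in every arm, observed difference = f × true difference. For assumed rates of 4% and 12%, the difference of 8 points becomes 0.5 × 8 = 4 points at f = 0.5.

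*Chance of getting an interval.* The threshold applies to any group, so

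P(interval) = 1 − ∏ P(Xᵢ ≤ 3), with Xᵢ ~ Binomial(nᵢ, p·f) and arms independent.

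Arm sizes:
- Cohort A: 25 in each of 4 arms (protocol 4.1).
- Cohort B, with Parts 1 and 2 pooled because safety is summarised by cohort and intervention group, and no dose adaptation: Part 1 has 60 randomised 2:1, so 40 on 100 mg and 20 on placebo. Part 2 has 280/4 = 70 per arm (protocol 9.2). Placebo is 20 + 70 = 90, 25 mg is 70, 50 mg is 70, and 100 mg is 40 + 70 = 110.

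Worked cases:
- Cohort A, p = 10%, all counted: P(X ≤ 3) = 0.7636 per arm; 1 − 0.7636⁴ = 0.66.
- Cohort A, p = 10%, half flagged (effective rate 5%): P(X ≤ 3) = 0.9659; 1 − 0.9659⁴ = 0.13.
- Cohort B, p = 10%, half flagged (effective rate 5%): 1 − 0.3358 × 0.5339² × 0.1945 = 0.98.
- Cohort B, p = 5%, half flagged (effective rate 2.5%): 1 − 0.8114 × 0.9017² × 0.7038 = 0.54.

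| | p | All counted | 75% flagged | 50% flagged | 25% flagged |
|---|---|---|---|---|---|
| Cohort A | 10% | 0.66 | 0.38 | 0.13 | 0.01 |
| Cohort A | 5% | 0.13 | 0.05 | 0.01 | <0.01 |
| Cohort B, pooled | 10% | >0.99 | >0.99 | 0.98 | 0.54 |
| Cohort B, pooled | 5% | 0.98 | 0.88 | 0.54 | 0.10 |

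**The case against.** **The SAP's own definition has no causality term.** Sections 15.1.1 and 15.2.3 both name the AESI simply as Grade ≥ 3 severe infection, and the category rule is class plus grade. The authors may well have meant every such infection. That stands as a statement of intent, but the operative selection sentence is the flag, and a program written to the text would start there.

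**Sites may flag unrelated events anyway.** Protocol 2.3.1 points that way. Section 8.3.7 itself bases its AESI list on mode of action and toxicology and says that AESIs may need evaluation to understand the association with treatment. The AESI reporting rules in Appendix 4 mention no causality condition. The list in 8.3.7 is not visible in the public text, and the CRF completion conventions are a separate document. A reader might infer that every severe infection judged unrelated is certain to drop out. The documents do not support that; they support only that it may, depending on which text a site follows.

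**The counts are reported anyway.** This is correct. The infections row of the worst-grade table gives the pooled number of participants by arm, whatever the causality, so an undercounted AESI table could be noticed. It would be wrong to infer that severe infections disappear from safety reporting. What may be incomplete is the AESI endpoint and its planned risk difference.

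**The threshold is not arm by arm.** A reader might suppose that one arm falling from, say, 6 affected participants to 2 loses the interval. It does so only if every other group is also below 4.

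**Conclusion.** The point holds in a limited form. The AESI comparison depends on an investigator flag whose meaning the protocol states in two incompatible ways. Under one of them, Grade ≥ 3 infections judged unrelated are left out of a named secondary safety endpoint.

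The size of the loss is unknown. If the flagged share is equal across arms, the risk difference shrinks in proportion to it. Loss of the interval is mainly a concern for Cohort A, or for low event or flagging rates. At an assumed 10% rate with half flagged, the chance of an interval falls from 0.66 to 0.13 in Cohort A but stays at about 0.98 in pooled Cohort B. These figures rest on assumed rates and flagging shares, equal rates across arms, independence between arms and no dose adaptation.

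The change is still worth making because it is cheap and takes a subjective filter out of a randomised comparison.

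**What to change.** 1. In SAP 15.2.3, derive the severe-infection AESI from all treatment-emergent events with primary SOC Infections and Infestations and CTCAE Grade ≥ 3, regardless of flag or causality. Use this set for Tier 1 in 15.1.1.
2. Show the flagged events and the related events as a supportive split, with a listing that reconciles flag against derivation.
3. Reconcile the AESI wording of protocol 8.3.7 with 2.3.1 so that the flag has one meaning at all sites.
4. In SAP 15.1.1, reword the Tier 1 severe-infections line so that its mention of preferred terms cannot be read as a causality restriction.

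**Cost.** Items 1, 2 and 4 need SAP wording and one derived variable from data already collected (SOC, grade, onset date). Item 3 touches a protocol section that also governs 24-hour AESI reporting, so it needs protocol wording and site communication; the analysis change does not have to wait for it. The reported AESI rate may be higher than the flagged one.

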15.3 Clinical Laboratory Evaluation

All laboratory values will be reported in SI units. Time window will be applied to laboratory assessments (see section 9.7).

Laboratory values (including corresponding normal ranges) from the central laboratory will be used for summary statistics and shift tables.

In case both central and local labs are collected, summary statistics will be based on central lab collected data, while summaries of worst on-treatment abnormalities will be based on both local and central lab data.

Laboratory results will be graded according to NCI-CTCAE version 5.0. Laboratory parameters which cannot be graded per NCI-CTCAE will be presented according to the categories: below normal limit, within normal limits and above normal limit (according to the laboratory normal ranges).

The definition of baseline measurement is provided in section 9.2.

Values below the detection limit will be imputed by half of the detection limit. If a text value with an "> x" is reported it will be analyzed as +1 significant digit, e.g., "> 7.2 mmol" will be analyzed as 7.3.

Quantitative data (hematology, biochemistry, coagulation and urinalysis) will be summarized using descriptive statistics (n, mean, SD, median, Q1, Q3, minimum, and maximum) of raw values and absolute changes from baseline at each on-treatment scheduled visit.

Qualitative data (hematology, biochemistry and coagulation) based on reference ranges will be described according to the categories (i.e., low, normal, high). For urinallysis parameters, the classification Normal, Trace/+, ++, ++++ will be used instead.

Abnormalities classified according to NCI-CTCAE toxicity grading version 5.0 will be described using the worst on-treatment grade. Unless otherwise specified, number of participants with missing measurements will be presented as separate category. For those parameters which are graded with two directions of toxicities such as potassium (hypokalemia/hyperkalemia), the toxicities will be summarized

CONFIDENTIAL

INFORMATION

separately. Low direction toxicity (e.g., hypokalemia) grades at Baseline and post-baseline will be set to 0 when the variables are derived for summarizing high direction toxicity (e.g., hyperkalemia), and vice versa. The same applies for non-gradable parameter, and description of changes from Normal/Low to High and Normal/High to Low will be provided, accordingly. The direction of parameters can be found in the MS ADaM template, except for eGFR for which the worst post-baseline value will be considered as the lowest value, and CO₂ for which the worst post-baseline value will be considered in the two directions (both lowest and highest values).

For **WBC** differential counts (total neutrophil [including bands], lymphocyte, monocyte, eosinophil, and basophil counts), the absolute value will be used when reported. When only percentages are available (this is mainly important for neutrophils and lymphocytes, because the CTCAE grading is based on the absolute counts), the absolute value is derived as follows:

Derived differential absolute count = (WBC count) * (Differential % value / 100)

If the range for the differential absolute count is not available (only range for value in % is available) then Grade 1 will be attributed to as follows:

• Lymphocyte count decreased:

derived absolute count does not meet Grade 2-4 criteria, and

% value < % LLN value, and

derived absolute count $\geq 800/\text{mm}^3$

• Neutrophil count decreased

derived absolute count does not meet Grade 2-4 criteria, and

% value < % LLN value, and

derived absolute count ≥ 1500/mm³

For **calcium**, CTCAE grading is based on Corrected Calcium and Ionized Calcium (CALCIO), if available. Corrected Calcium is calculated from Albumin and Calcium as follows

```
Corrected calcium (mmol/L) = measured total calcium (mmol/L) + 0.02 (40 - serum albumin [g/L])
```

Liver function tests: Alanine aminotransferase (ALT), aspartate aminotransferase (AST), and total bilirubin are used to assess possible drug induced liver toxicity. The ratios of test result over upper limit of normal (ULN) will be calculated and classified for these three parameters during the on-treatment period.

Summary of liver function tests will include the categories listed below. The number and percentage of participants with each of the following during the on-treatment period will be summarized by study intervention group:

- ALT \geq 3×ULN, ALT \geq 5×ULN, ALT \geq 10×ULN, ALT \geq 20×ULN
- AST $\geq 3 \times ULN$, AST $\geq 5 \times ULN$, AST $\geq 10 \times ULN$, AST $\geq 20 \times ULN$

- (ALT or AST) \geq 3×ULN, (ALT or AST) \geq 5×ULN, (ALT or AST) \geq 10×ULN, (ALT or AST) \geq 20×ULN
- TBILI > 2×ULN
- Concurrent ALT \geq 3×ULN and TBILI \geq 2×ULN (*)
- Concurrent AST $\geq 3 \times ULN$ and TBILI $\geq 2 \times ULN$ (*)
- Concurrent (ALT or AST) $\geq 3 \times ULN$ and TBILI $\geq 2 \times ULN$ (*)
- Concurrent (ALT or AST) $\geq 3 \times ULN$ and TBILI $\geq 2 \times ULN$ and ALP $\geq 2 \times ULN$ (*)
- Concurrent (ALT or AST) $\geq 3 \times ULN$ and TBILI $\geq 2 \times ULN$ and ALP $\leq 2 \times ULN$ or missing (*)

Concurrent measurements are those occurring on the same date.

Categories will be cumulative, i.e., a participant with an elevation of AST \geq 10×ULN will also appear in the categories \geq 5×ULN and \geq 3×ULN. Liver function elevation and possible Hy's Law cases will be summarized using frequency and percentage.

An evaluation of drug-induced serious hepatotoxicity (eDISH) plot will also be created, with different symbols for different study intervention groups, by graphically displaying two figures with log-scale transformed axes presented as:

- Peak serum ALT (/ULN) vs peak total bilirubin (/ULN) during the on-treatment period including reference lines at ALT = 3×ULN and total bilirubin = 2×ULN
- Peak serum AST (/ULN) vs peak total bilirubin (/ULN) during the on-treatment period including reference lines at AST = 3×ULN and total bilirubin = 2×ULN

In addition, a listing of all TBILI, ALT, AST and ALP values for participants with a post-baseline TBILI $\geq 2 \times \text{ULN}$, ALT $\geq 3 \times \text{ULN}$ or AST $\geq 3 \times \text{ULN}$ will be provided.

Analysis for Parameters with NCI-CTCAE Grade Available

The laboratory toxicities will be tabulated using descriptive statistics (number of participants and percentages) during the on-treatment period. Grade 0 is not defined per NCI-CTCAE but will be used in derivations for simplicity to indicate that evaluable measurements are available. Laboratory values within normal range but considered grade 1 according to NCI-CTCAE will not be graded 1 (Grade 0, instead).

- A summary table of laboratory parameters (excluding amylase) by NCI-CTCAE grade will include number and percentage of participants with at least one value of Grade ≥ 0, Grade ≥ 3, Grade ≥ 4 during the on-treatment period.
- A shift table will summarize baseline NCI-CTCAE grade versus the worst on-treatment NCI-CTCAE grade (excluding amylase). The highest NCI-CTCAE grade during the on-treatment period is considered as the worst grade for the summary. (*)

In case of gradings involving baseline measurements (parameters identified with a start [*] below) for the identification of grades during the on-treatment period, the shift table will present baseline normal and abnormal. Normal will include measurements below and within normal range (direction

increase), or measurements within and above normal range (direction decrease). In case of missing baseline values, the on-treatment grades will be generated assuming the baseline was normal.

The above analyses apply to hematology and chemistry evaluations which can be graded per NCI-CTCAE:

Hematology

Hemoglobin (HB) (anemia/ hemoglobin increased), Leukocytes (white blood cell decreased/ leukocytosis), Lymphocytes (lymphocyte count increased/decreased), Neutrophils / Absolute Neutrophils Count (ANC) (neutrophil count decreased), Platelet Count (PLT) (platelet count decreased), Eosinophils * (eosinophilia).

• Coagulation

INR * (INR increased), Activated partial thromboplastin time (aPTT prolonged)

• Serum chemistry

Albumin (hypoalbuminemia), Alkaline Phosphatase * (alkaline phosphatase increased), Alanine Aminotransferase * (ALT) (ALT increased), Aspartate Aminotransferase * (AST) (AST increased), Total Bilirubin * (blood bilirubin increased), Creatinine * (creatinine increased), Potassium (hypokalemia/ hyperkalemia), Sodium (hyponatremia/ hypernatremia), Calcium (hypocalcemia/hypercalcemia), Glucose (hypoglycemia), Gamma Glutamyl Transferase * (GGT) (GGT increased), eGFR (chronic kidney disease), Amylase (serum amylase increased), Lipase (lipase increased), Bicarbonate (blood bicarbonate decreased).

Analysis for Parameters with NCI-CTCAE Grade not Available

Hematology, chemistry (excluding amylase) and urinalysis evaluations which cannot be graded per NCI-CTCAE criteria will be summarized as frequency (number and row percentage) of participants as follows:

- Shifts from baseline normal to at least one result above normal during on-treatment period (*)
- Shifts from baseline normal to at least one result below normal during on-treatment period (*)

This applies to the following parameters:

Hematology

Hematocrit (low/high), Mean Corpuscular Hemoglobin (MCH) (low), Mean Corpuscular Volume (MCV) (low/high), monocytes (high), basophils (high), Erythrocyte Sedimentation Rate (ESR) (high)

Coagulation

Prothrombin time (low/high)

• Serum chemistry

Chloride (low/high), Total Protein (low/high), Blood Urea Nitrogen (high), C-reactive Protein (CRP) (high)

Urinalysis

CONFIDENTIAL INFORMATION

pH (low [< 4.5]/high [≥ 9]), specific gravity (low [≤ 1.005]/high [≥ 1.030]), glucose (trace/1+, 2+, 3+, 4+), protein (trace/1+, 2+, 3+, 4+), occult blood (trace/1+, 2+, 3+, 4+), ketones (trace/1+, 2+, 3+, 4+), bilirubin (trace/1+, 2+, 3+, 4+), urobilinogen (trace/1+, 2+, 3+, 4+), nitrite (trace/1+, 2+, 3+, 4+), leukocyte esterase (trace/1+, 2+, 3+, 4+)

CCL

Microscopic data (except UPCR), serum and urine pregnancy test results collected during the study will be listed.

The following figures will be provided for hematology, coagulation, serum chemistry (amylase excluded) parameters, CCI

- Boxplots of the laboratory values (by study intervention group) by timepoint
- Boxplots of the change from baseline by timepoint
 Where applicable, reference lines for NCI-CTCAE grades should be added to graphical displays.

Listings of laboratory results will be provided for all laboratory parameters. The listings will be sorted by study intervention, parameter and assessment date or visit for each participant. Laboratory values that are outside the normal range will also be flagged in the data listings, along with corresponding normal ranges and NCI-CTCAE grades.

